4. EVALUATION INDICATORS

- 4.1 Effectiveness evaluation indicators
- 4.1.1 Primary effectiveness indicators

> Overall performance of catheter flushing and/or locking

Definition: The success rate of pre-filled flush syringe for flushing and/or locking the catheter.

Observation time: At the time of preparation, initiation, implementation, and completion of catheter flushing and/or locking.

Evaluation criteria: The success rate of flushing and/or locking the catheter = (number of cases evaluated as "pass"/total number of cases evaluated) \times 100%.

Evaluation method:

Overall performance is assessed by the nurse, who is required to answer the following questions:

- 1) Whether the air in the pre-filled flush syringe can be removed successfully?
- 2) Whether the pre-filled flush syringe can be connected to the catheter smoothly?
- 3) Whether the pre-filled flush syringe can flush and/or lock the catheter successfully?
- 4) Whether the pre-filled flush syringe can be disconnected from the catheter smoothly?

5) Whether any sites of the flush syringe leak at any time during use?

The overall performance of catheter locking and flushing is only considered "pass" only if:

Questions 1 to 4 are answered "Yes" and question 5 is answered "No".

Reason for indicator selection: The effectiveness of the product is reflected in five main aspects: venting, catheter connection, catheter flushing and/or locking, disconnection from the catheter, and the presence of leaks.

Precautions: None.

4.1.2 Secondary effectiveness indicators

Ease of pushing of the plunger during catheter flushing and/or locking

Definition: The pushability of the plunger when the pre-filled flush syringe is flushing and/or locking.

Observation time: At the time of implementation and completion of catheter flushing and/or locking.

Evaluation criteria: Ease of pushing of the plunger during catheter flushing and/or locking = (number of cases whose score ≥ 3 /total number of cases evaluated) $\times 100\%$.

Evaluation method:

As assessed by a nurse, who is asked to answer the following questions:

Whether it is easy to push the plunger (ease of pushing) during catheter flushing and/or locking?

5-score scale:

- 5 scores: Very easy;
- 3 scores: Easy;
- 1 score: Difficult.
- 4.2 Safety indicators
- Adverse events and serious adverse events.

4.3 Other indicators

> Record device deficiencies that occur during the trial.

5. STATISTICAL ANALYSIS DATASETS

5.1 Full analysis set (FAS)

Dataset consisting of all subjects randomized and grouped according to the basic principles of intention-to-treat analysis.

Subjects are analyzed in randomly assigned treatment groups according to the intention-to-treat principle.

FAS is used as the population for analysis of baseline information in this study and also as the population for effectiveness evaluation.

5.2 Per protocol set (PPS)

Dataset consisting of subjects in the FAS with no serious violations of the test protocol*, good compliance, and no missing primary effectiveness indicators.

PPS is used as the primary population for the analysis of the primary effectiveness indicators in this study.

Note: *"No serious violations of the trial protocol" refers to violations of the trial protocol that do not affect the primary effectiveness evaluation.

5.3 Safety set (SS)

Dataset consisting of all subjects who have received at least one treatment with the investigational devices and had at least one safety evaluation."

Safety analysis is performed according to the actual assigned treatment groups.

SS is used as the primary population for the safety analysis in this study.

6. STATISTICAL ANALYSIS METHODS

6.1 General principles

This study will use SAS 9.4 software or the higher version for statistical analysis.

All statistical tests are conducted using two-sided tests and a P-value less than 0.05 will be considered statistically significant (unless otherwise specified). In this study, hypotheses and statistical inferences are made only for the primary effectiveness indicators, and the intergroup comparisons for the remaining indicators are exploratory analyses.

For the description of quantitative indicators, the number of cases (missing), mean, standard deviation, median, minimum, maximum, and first quartile and third quartile are calculated. The decimal places of the minimum and maximum are kept the same as the original data, but the decimal places of the mean, standard deviation, and median are one more than the original data, but usually, the maximum number of decimal places does not exceed four decimal places.

Qualitative indicators are described by the number of cases and percentages of each category. The percentages are calculated using the non-missing data in each analysis set. Percentages are retained to one decimal place.

All numerically derived variables are retained to two decimal places, unless otherwise specified.

The treatment of missing data will be described in Section 7, otherwise all missing data will be left unfilled.

6.2 Subject profile

6.2.1 Enrollment and progress

Summarize the number of individuals who have been screened, failed to be screened, and successfully been screened (randomized, non-randomized), and summarize the reasons for failure of subjects who failed the screening.

Summarize the number and proportion of subjects in each group in the randomized population who have not use the investigational device, used the investigational device, completed the trial, not complete the trial, and entered each analysis set (FAS, PPS, SS), and summarize in detail the main reason for non-completion for subjects who fail to complete the trial on the end page.

Summarize the number and proportion of subjects randomized into each analysis set (FAS, PPS, SS) by site.

List the details of subject screening, and subject completion of the trial in the randomized population. List details of subjects who are not included in the PPS and those who deviate from the protocol.

6.2.2 General information

- (1) Evaluation Indicators
 - 1) Demographics and vital signs: Age, gender, ethnicity, body temperature, pulse, respiration, systolic blood pressure, diastolic blood pressure;
 - 2) Treatment procedure: The procedures to be performed with the investigational device, the vascular access device and its placement.
- (2) Evaluation method

FAS is used for evaluation.

The age, body temperature, pulse, respiration and systolic blood pressure are quantitatively described, and the t-test/Wilcoxon rank sum test is used for comparison between groups; the gender, ethnicity, procedures to be performed with the inestigational device, vascular access device and its placement are qualitatively described, and the chi-square test/Fisher exact probability method is used for comparison between groups.

6.2.3 Intervention and treatment compliance

6.2.3.1 Investigational devices

Based on FAS, quantitative descriptive statistics (number of cases, mean, standard deviation, median, first quartile and third quartile, minimum, and maximum) shall be used to describe the duration of investigational device use in each group. Qualitative descriptions of whether the drug is used before investigational device use during the trial (via the same vascular access) and whether the drug is used after investigational device use during the trial (via the same vascular access) shall be performed.

Duration of investigational device use (secs) = end of use - start of use.

6.2.3.2 Combined medication

Prior medication is defined as combined medication prior to the start of investigational device use. Concomitant medication is defined as combined medication at or after the start of investigational device use. All combined medications are listed in the form of a list.

6.3 Effectiveness evaluation

6.3.1 Primary effectiveness evaluation

(1) Evaluation Indicators

Overall performance of catheter locking and/or flushing is considered "**pass**" only if: Questions 1 to 4 are answered "Yes" and question 5 is answered "No".

Subjects who do not answer any of questions 1-5 or who answer "not applicable (NA)" will not be entered into the per protocol set; they will be treated in accordance with Table 6.1 when entering the full analysis set.

Table 6.1 Definition of "pass" for different scenarios of primary effectiveness indicators

Questions related to the primary effectiveness indicators	Scenario 1	Scenario 2	Scenario 3	Scenario 4
Whether the effectiveness evaluation is performed?	No	Yes	Yes	Yes
 Whether the air in the pre-filled flush syringe can be removed successfully? Whether the pre-filled flush syringe can be connected to the catheter smoothly? Whether the pre-filled flush syringe can flush and/or lock the catheter successfully? Whether the pre-filled flush syringe can be disconnected from the catheter smoothly? 	NA	Yes	At least one of the answers is "No" for questions 1-4, or "Yes" for question 5	At least one of the answers in Scenario 2 is "NA" or not selected
5. Whether any sites of the flush syringe leak at any time during use?		No		
Primary effectiveness determination (pass/fail)	Missing	Pass	Fail	Missing
Whether to be included in FAS	Yes	Yes	Yes	Yes
Whether to be included in PPS	No	Yes	Yes	No

(2) Evaluation method

The study hypotheses for the primary evaluation indicators are:

Null hypothesis H₀: The overall performance pass rate p_1 in the test device group is inferior to p_2 in the control device group ($p1 \le p2-\delta$);

Alternative hypothesis H₁: The overall performance pass rate p_1 of the test device group is not inferior to p_2 of the control device group $(p_1 > p_2 - \delta)$.

Where $\delta = 5\%$ is the non-inferiority margin, i.e., the range of differences considered not clinically significant.

FAS and PPS are used for evaluation.

Main analysis:

Describe the number and percentage of subjects for whom the two kind of pre-filled flush syringes are used to flush and/or lock the catheter successfully for groups in each study site and all study sites.

For the primary effectiveness indicator, i.e., overall performance of catheter flushing and/or locking, intergroup comparisons are performed using the Breslow-Day test for parity of effectiveness across sites. The Breslow-Day test is not required if the rate is 100% for both groups in each site, and the effectiveness is considered not statistically different between sites.

A Breslow-Day test with a P > 0.05 means that there is no statistical difference between sites, and the effectiveness data of each site can be combined for analysis. For the difference in the pass rate of the pre-filled flush syringes used to flush and/or lock the catheter in the combined test and control device groups, the 95% confidence interval (CI) for the difference in the pass rate between the two groups is calculated using the Wald method.

A Breslow-Day test with a $P \le 0.05$ indicates a statistical difference between sites, and that the effectiveness data may not be combined for analysis and need to be statistically described separately for each site. Point estimates corrected for site factors are obtained by weighting the difference in the pass rate of the pre-filled flush syringes used to flush and/or lock the catheter by the minimal risk method^[1] for the test device group and the control device group in each site, and the 95% confidence interval (CI) for the difference in the pass rate between the two groups is calculated using the Wald method.

If the pass rate is 100% in both groups, the Newcombe Wilson method ^[2] is used to calculate the 95% confidence interval (CI) for the difference in the pass rate between the two groups.

If the results show that the lower limit of the bilateral 95% confidence interval (CI) for the difference in the pass rate between the test device group and the control device group for pre-filled flush syringes used to flush and/or lock the catheter is greater than -5% (a pre-defined non-inferiority limit), H_0 is rejected and the test device group can be considered non-inferior to the control device group in terms of overall performance pass rate.

The procedure code for calculating confidence interval (CI) about the site-adjusted CMH rate difference is shown below:

/*Variable description: dataset is the input dataset, siteid represents the study site, nurseid represents the nurse, trtp represents the treatment factor, y represents the outcome variable*/

data dataset;

set dataset;

if group="test group" then trt=1;else trt=2;

/*group is the group variable in the analyzed dataset, and "test group" is generally the value of the group variable, which represents the investigational test device*/

if main="pass" then var=1;else var=2;

/*main is the analyzed variable, and "pass" is generally the dichotomous value of the main variable, which represents the study effect */

run; ods select print; ods output CrossTabFreqs=CrossTabFreqs; proc freq data=dataset; table siteid*trt*var.*Generate a four-cell table; run: quit; proc sort data = dataset; by siteid trt; run; ods select print; ods output BinomialCLs=BinomialCLs; proc freq data=a; by siteid trt; table var/bin(cl=wilson level="1");*Wilson confidence interval is generated in preparation for newcombe method; run; quit; /******Calculate site-adjusted CMH rate difference by using the minimum risk method*** ****************************** proc sql undo policy=none; create table n11 as

select distinct siteid, Frequency as n11

```
from CrossTabFreqs where trt=1 and var=1;
quit;
proc sql undo policy=none;
  create table n12 as
    select distinct siteid, Frequency as n12
    from CrossTabFreqs where trt=1 and var=2;
  ;
quit;
proc sql undo policy=none;
  create table n21 as
     select distinct siteid, Frequency as n21
    from CrossTabFreqs where trt=2 and var=1;
quit;
proc sql undo policy=none;
  create table n22 as
     select distinct siteid, Frequency as n22
    from CrossTabFreqs where trt=2 and var=2;
quit;
data n1234;
  merge n11 n12 n21 n22;*Generate the number of four cells in a four-cell table;
  p1=n11/sum(n11,n12);p2=n21/sum(n21,n22);*Calculate the pass rates of test and control groups: p1,p2;
  p1 p2=p1-p2;
  n=sum(n11,n12,n21,n22);
  diffn=p1 p2*n;
  var=p1*(1-p1)/sum(n11,n12)+p2*(1-p2)/sum(n21,n22); *The variance of the rate difference;
  if var=0 then var 1=1;else var 1=1/var;
 ***If both groups of studies are analyzed at 100%, the variance of the rate difference is 0 and the inverse of
the variance is set to 1:
  dvar 1=p1 p2*var 1;
run;
proc sql undo_policy=none;
  create table riskdiff0 as
    select *,sum(n) as s n,sum(diffn) as s diffn,
        sum(var 1) as s var 1,sum(dvar 1) as s dvar 1
    from n1234;
quit;
data riskdiff;
  set riskdiff0;
  alaph=diffn*s var 1-s dvar 1;
  beta=var 1*(1+alaph*s diffn/s n);
run;
proc sql undo policy=none;
  create table riskdiff as
     select *, sum(alaph*dvar 1) as s advar 1,
        sum(beta*p1_p2) as s_betadif
    from riskdiff;
quit;
data riskdiff;
  set riskdiff:
  w_diff=beta/s_var_1-(alaph*var_1/(s_var_1+s_advar_1))*(s_betadif/s_var_1);***Calculate the weights
  for rate difference in each site by the minimal risk method;
run;
proc sql undo policy=none;
  create table a riskdiff as
     select *,sum(p1 p2*w diff) as a riskdiff
```

from riskdiff:

```
quit;**Perform weighted estimation of the rate difference between the two groups in each site;
/*****Calculate the confidence interval of rate difference by using Newcombe
                                                                                        and Wald
                               ****
method**
data BinomialCLs1 BinomialCLs2;
  set BinomialCLs;
  if trt=1 then output BinomialCLs1;
  if trt=2 then output BinomialCLs2;
run;
data newcombe0;
merge a riskdiff
BinomialCLs1(keep=siteid LowerCL uppercl
              rename=(LowerCL=LowerCL1 uppercl=uppercl1))
BinomialCLs2(keep=siteid LowerCL uppercl
              rename=(LowerCL=LowerCL2 uppercl=uppercl2));
run;
proc sql undo policy=none;
  create table newcombe as
    select *,sum(LowerCL1*(1-LowerCL1)*w diff**2/sum(n11,n12)) as part1,
          sum(uppercl2*(1-uppercl2)*w_diff**2/sum(n21,n22)) as part2,
          sum(LowerCL2*(1-LowerCL2)*w diff**2/sum(n21,n22)) as part3,
          sum(uppercl1*(1-uppercl1)*w diff**2/sum(n11,n12)) as part4,
          sum(w diff*var) as part
    from newcombe0
quit;* Calculate the prepared parts of the formula by using newcombe and wald methods;
data newcombe wald:
  set newcombe;
  a newcombe l=a riskdiff-probit(1-0.025)*sqrt(part1+part2);
  a newcombe u=a riskdiff+probit(1-0.025)*sqrt(part3+part4):
  a wald l=a riskdiff-probit(1-0.025)*sqrt(part);
  a wald u=a riskdiff+probit(1-0.025)*sqrt(part);
run;*Substitute into the formula;
```

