6.2 Analysis data sets

Full analysis set (FAS): a data set consisting of all randomized subjects according to the basic principle of intention-to-treat analysis.

Per protocol set (PPS): refers to the subjects in the FAS who are of no serious violation against

the trial protocol, good compliance, and no missing primary efficacy indicators.

Safety set (SS): refers to the subjects who receive at least one study device treatment and at least one safety evaluation.

Efficacy analysis is to be performed based on the full analysis set and per protocol set. PPS will be used as the primary population for analyzing primary efficacy indicators in this study; FAS will be used as the population for analyzing the baseline data of this study, as well as for efficacy evaluation. SS will be used as the primary population for the safety analysis in this study.

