6.3 Subject exclusion criteria

Investigators, sponsors, data management and statistical analysis units comprehensively judge whether to exclude patients based on factors such as the degree to which subjects completed the trial and the reasons for withdrawal. FAS subjects shall be excluded from PPS if they meet one of the following:

- (1) Subjects who do not meet the inclusion criteria or meet any of the exclusion criteria are mistakenly included in the trial;
- (2) Subjects with missing primary efficacy indicators;
- (3) Subjects who are in major violation of the trial protocol and with poor compliance;
- (4) Subjects with other special reasons.

Specific subject exclusion will be determined through discussion between the investigator, sponsor, data administrator and statistician at the data review meeting.

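### SAP 6.3.1 keeps a record with both a failing answer and an NA out of the PPS in its text, but in the PPS as a Fail in Table 6.1, and does not say which governs

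*SAP*

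**What the plan says.** The primary outcome is a pass only if questions 1 to 4 are answered yes and question 5 (leakage) is answered no. SAP 6.3.1 then handles incomplete answers twice.

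- The sentence above Table 6.1: "Subjects who do not answer any of questions 1-5 or who answer 'not applicable (NA)' will not be entered into the per protocol set". It continues that "they will be treated in accordance with Table 6.1 when entering the full analysis set". The table is invoked for the FAS only.
- Table 6.1 has its own PPS row. Scenario 3 ("At least one of the answers is 'No' for questions 1-4, or 'Yes' for question 5") gives Fail, FAS yes, PPS yes. Scenario 4 ("At least one of the answers in Scenario 2 is 'NA' or not selected") gives Missing, FAS yes, PPS no.

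SAP 5.2 defines the PPS by no serious violation, "good compliance, and no missing primary effectiveness indicators", and adds that "PPS is used as the primary population for the analysis of the primary effectiveness indicators in this study". Protocol 6.2 uses nearly the same definition ("good compliance, and no missing primary efficacy indicators"). Protocol 6.3 lists "Subjects with missing primary efficacy indicators" among the reasons to leave the PPS. None of these places says whether a record with a failing answer and an NA counts as missing.

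**The concern.** A pass needs all five answers to be right, so one failing answer already settles that the record is not a pass, whatever the other items say. The sentence would nevertheless drop that record from the PPS because another item is NA. The subjects dropped this way are all failures, so the exclusion depends on the outcome and acts on the primary population.

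Such records are plausible. Scenario 4 shows that the SAP expects item-level NA answers in an evaluation that was performed. Protocol 5.5.2 does not allow the device to be changed after priming, so an early failure could leave later questions not applicable. That last step is an inference.

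The trial is open-label (Protocol 5.1), PPS exclusions are settled at a data review meeting that includes the sponsor (Protocol 6.3), and blind review is stated as not applicable (Protocol 8.8). Whether an observed failure counts in the primary analysis should not be left to that meeting.

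**Working it through.** **1. The two rules side by side**

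| Record | Sentence above Table 6.1 | Table 6.1 |
|---|---|---|
| All five items answered, none failing | in PPS | Scenario 2: Pass, in PPS |
| All five answered, at least one failing | in PPS | Scenario 3: Fail, in PPS |
| No failing answer, at least one NA | out of PPS | Scenario 4: Missing, out of PPS |
| At least one failing answer and at least one NA | **out of PPS** | Scenario 3: **Fail, in PPS** |

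Only the last row conflicts. Scenario 4 can be read in two ways:

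- As otherwise-passing records with a gap, since it refers back to Scenario 2. The table is then coherent, and it contradicts the sentence.
- As any record with an NA. The mixed record then meets Scenarios 3 and 4 at once, and its FAS status (Fail or Missing) is open too.

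For blank items, the sentence can mean that no question was answered or that at least one was not. The separate NA clause catches the mixed record on either reading.

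**2. Inputs for the size**

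From the documents: 98% success in both arms, margin 5%, one-sided alpha 0.025, 90% power, 10% dropout, 63 nurses with 6 devices each, and a Wald two-sided 95% interval when sites are pooled (SAP 3.2, 6.3.1).

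The plan's own sample size reproduces:

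- n = (1.960 + 1.282)² × 2 × 0.98 × 0.02 / 0.05² = 164.8, so 165 per arm.
- 165 / 0.9 = 183.3, so 184 per arm and 368 in total.
- 63 × 6 = 378, or 189 per arm, which is used below.

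Assumed, because the documents do not give it: q, the share of failures that also carry an NA, set to 0%, 5% and 10%.

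**3. Expected number of mixed records at 98% v 98%**

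378 × 0.02 × q = 0, 0.38 and 0.76. The chance of at least one is 1 − (1 − 0.02q)^378 = 0%, 31% and 53%.

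**4. Effect on the conclusion**

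The number of failures in each arm is binomial with n = 189. Under the sentence, each failure is removed from numerator and denominator with probability q. Non-inferiority is shown if d − 1.96 × √[p₁(1−p₁)/n₁ + p₂(1−p₂)/n₂] > −5%, where d = p₁ − p₂. All outcomes are enumerated exactly. The last two columns compare the sentence with the table rule for the same data.

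| True success, test v control | q | Non-inferiority shown | Changed towards | Changed away |
|---|---|---|---|---|
| 98% v 98% | 0% | 91.85% | – | – |
| | 5% | 92.66% | 1.22% | 0.41% |
| | 10% | 93.52% | 2.28% | 0.61% |
| 93% v 98% (at the margin) | 0% | 3.90% | – | – |
| | 5% | 4.79% | 1.11% | 0.22% |
| | 10% | 5.99% | 2.40% | 0.30% |

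The 3.90% at q = 0 exceeds 2.5% because of the Wald interval, not because of this rule. If the 10% share applies to one arm only, the figure at the margin is 6.93% (test arm) or 3.27% (control arm).

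**5. Single-record examples, Wald lower limit**

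- 7/189 test v 3/189 control failures: −2.116% − 1.96 × 1.647% = −5.345%, not shown. With one mixed test-arm record excluded (6/188 v 3/189): −1.604% − 1.96 × 1.572% = −4.684%, shown.
- 7/189 v 4/189: −1.587% − 1.96 × 1.727% = −4.973%, shown. With one mixed control-arm record excluded (7/189 v 3/188): −2.108% − 1.96 × 1.650% = −5.342%, not shown.
- 4/189 v 4/189, the expected counts rounded: −2.9%, far from the margin.

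**The case against.** The best reply is that the intended rule can be recovered. Scenario 4 is worded as a departure from the all-pass pattern, so on its natural reading it does not overlap with Scenario 3. The table's PPS row would serve little purpose if the table governed only the FAS. SAP 5.2 and Protocol 6.2 and 6.3 name only a missing primary indicator as the outcome-related reason to leave the PPS, and a record with a failing answer has a determined outcome. On this view the sentence is a loose summary of Scenarios 1 and 4.

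The size also rests on an assumed q. At q = 1% the conclusion changes in only 0.36% of trials at 98% v 98% (0.26% towards, 0.10% away), and false non-inferiority at the margin moves from 3.90% to 4.05%. The one-record examples are chosen near the boundary: at 2% failure per arm, exactly 7 v 3 and exactly 7 v 4 each have a probability of about 1.0%. The FAS is analysed as well, and SAP 6.2.1 lists every subject left out of the PPS.

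Much of this stands. Scenario 3 is the likely intent, the FAS ambiguity needs the less natural reading of Scenario 4, and the effect is probably small. It does not remove the conflict. The sentence makes no exception for failing records, no text says that the table overrides it, and a programmer who follows it would drop failures from the primary population. The FAS result and the listing make the choice visible afterwards, but they do not fix the primary PPS result in advance.

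**Conclusion.** The concern holds and should be fixed before analysis. Confidence is high for the conflict in the text. The size depends on q, which the documents do not give. With q at 5% or 10% in both arms, 189 per arm and sites pooled, the two rules give different conclusions in 1.6% or 2.9% of trials at the planned rates, mostly towards non-inferiority. At the margin, false non-inferiority rises by 0.9 or 2.1 percentage points (4.79 − 3.90 and 5.99 − 3.90). The direction is not fixed: removing a test-arm failure favours the test device, and removing a control-arm failure works against it. If no mixed record occurs, there is no effect.

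**What to change.** Amend the sentence in SAP 6.3.1 so that Table 6.1 governs both the FAS and the PPS, and state the order:

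- Any No on questions 1 to 4, or Yes on question 5, is Fail and stays in the PPS unless the subject is excluded for another reason, whatever the other items say.
- A record is Missing and out of the PPS only if no evaluation was done, or if it has no failing answer and at least one item is NA or blank.

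Reword Scenario 4 to match, for example by limiting it to records with no failing answer.

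At the same time, check the program in SAP 6.3.1. It codes every value other than pass as the second category, so a Missing record left in the dataset would count as not passed, although SAP 7.1 leaves missing primary outcomes unfilled.

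The cost is one sentence and one table cell. No new data are needed.

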3.3.10 Cautions

- 1. Do not use if the packaging is incomplete.
- 2. Do not use if the pre-filled flush syringe is damaged and leaking.
- 3. Do not use if the nozzle cap is installed incorrectly or detached.
- 4. Do not use if any form of suspended particles is inspected visually or the solution is discolored, turbid, and precipitated.
- 5. Do not re-sterilize.
- 6. Check the expiration date on the packaging label and do not use if the product is expired.
- 7. Do not place the pre-filled flush syringe on a sterile interface or in sterile environment.
- 8. Do not reuse. Single use only. Discard any remaining parts of the unused.
- 9. Do not contact the solution with medicines incompatible. Please refer to the compatibility literature.

4. Trial Objective

To compare the BD PosiFlushTM Pre-filled Flush Syringes (manufactured by BD, USA) with the pre-filled flush syringes (manufactured by BD Medical Technology (Jiangsu) Co., Ltd.) and evaluate the effectiveness and safety for locking and flushing the end of catheter line.

5. Trial Design

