1) The operation shall be performed to flush and/or lock the end of the catheter line:

The procedure shall be performed to flush and/or lock the end of the catheter line by the study nurse. Refer to section 3.3.8 Usage for the specific operation method.

Record the time to start and end the flush syringe treatment.

Before the priming preparation, if device defects and other problems are found, each subject can change a new study device; if such problems are found after the priming preparation, each subject can only use the current one without changing the device.

2) Evaluation of effectiveness:

The use of the pre-filled flushing syringe shall be evaluated by the study nurse after flushing and/or locking the end of the catheter line. Refer to section 5.3.1 Evaluation of effectiveness for the specific evaluation method.

- 3) Record adverse events (AE/SAE);
- 4) Record combined medications/treatments;
- 5) Record device defects.

Follow-up

Follow-up is performed at 1 hour after the flush syringe treatment.

- 1) Record adverse events (AE/SAE);
- 2) Record combined medications/treatments.

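### SAP 6.3.1 gives two answers for a recorded device failure that also has an NA or blank item: Table 6.1 keeps it in the per protocol set, and the sentence above the table removes it

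*SAP*

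**What the plan says.** Both documents make the PPS primary for this endpoint. SAP 5.2: "PPS is used as the primary population for the analysis of the primary effectiveness indicators in this study". Protocol 6.2: "PPS will be used as the primary population for analyzing primary efficacy indicators in this study". The FAS is also analyzed.

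SAP 6.3.1 then handles incomplete questionnaires twice.

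- **Sentence above Table 6.1.** Subjects with an NA answer, or with items left unanswered, "will not be entered into the per protocol set; they will be treated in accordance with Table 6.1 when entering the full analysis set", and no exception is stated for a record that shows a failure.
- **Table 6.1, Scenario 3.** "At least one of the answers is 'No' for questions 1-4, or 'Yes' for question 5": Fail, in the FAS, in the PPS.
- **Table 6.1, Scenario 4.** "At least one of the answers in Scenario 2 is 'NA' or not selected": Missing, in the FAS, not in the PPS. Scenario 2 is the all-favorable pattern, so Scenario 4 describes a record with no adverse answer.
- **Table 6.1, Scenario 1.** No evaluation done: Missing, in the FAS, not in the PPS.

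SAP 7.1 leaves a missing primary outcome unfilled, and SAP 6.1 bases percentages on non-missing data. Protocol 6.3 settles individual PPS exclusions at a data review meeting that includes the investigator and the sponsor. The trial is open-label, and Protocol 8.8 lists blind review as not applicable.

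**The concern.** An early device failure is the kind of event that makes later questions inapplicable. If a primed syringe leaks before connection, a nurse may answer Yes to question 5 and NA to questions 2-4. The record documents a failure, but the sentence removes it from the primary set because of its NA items.

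Only about 3.8 failures per arm are expected at the planned 98% success rate, so single records can matter in a close result. With no stated precedence, the choice may fall to a meeting whose members can know the arm and the outcome. Removing test-arm failures, or the same share of failures from both arms, favors a non-inferiority claim.

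**Working it through.** **1. The texts applied to one record.** Question 1 Yes, questions 2-4 NA, question 5 Yes (leak):

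| Rule | FAS | PPS |
|---|---|---|
| Table 6.1, Scenario 3 | Fail | Included, Fail |
| Sentence above the table | Per Table 6.1: Fail | Excluded |

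They agree on the FAS and conflict on the PPS. Two alternative readings do not remove the conflict. If the unanswered-items clause covers only subjects who answered nothing, the NA clause still conflicts with Scenario 3. If Scenario 4 is read as any record with an NA or blank item, it overlaps Scenario 3, and one record is both Fail and Missing.

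**2. The plan's own figures.** Inputs from SAP 3.2: 98% in both arms, margin 5 points, one-sided alpha 0.025, power 90%, drop-out 10%.
- n per arm = (1.96 + 1.2816)² × 2 × 0.98 × 0.02 / 0.05² = 164.8, so 165, as stated.
- 165 / 0.9 = 183.3, so 184 per arm and 368 in total, as stated.
- 63 nurses × 6 uses = 378, or 189 per arm.
- Expected failures per arm: 189 × 0.02 = 3.8.

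**3. One record in a close result.** The SAP's Wald lower limit is d - 1.96 × sqrt(p1(1-p1)/n1 + p2(1-p2)/n2), with d the test minus control success rate. Non-inferiority needs a limit above -5%. The failure counts are chosen for illustration.

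| Failures, test v control | d | Lower limit | Non-inferior? |
|---|---|---|---|
| 7/189 v 3/189 (all counted) | -2.116 | -5.35% | No |
| 6/188 v 3/189 (one test failure dropped) | -1.604 | -4.68% | Yes |
| 6/188 v 2/188 (one dropped per arm) | -2.128 | -5.04% | No |

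First row: sqrt(0.0370 × 0.9630/189 + 0.0159 × 0.9841/189) = 0.01647, and -0.02116 - 1.96 × 0.01647 = -0.0535.

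The third row shows that losing an equal count per arm does not shrink the difference. It moves slightly away from zero, and the limit rises only because the variance falls.

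The same check was run from the smallest failing test count for each of 1 to 8 control failures. Dropping one test failure reverses the conclusion in 7 of 8 cases; dropping one per arm reverses 4 of 8, one of them only at -4.999%. These starting points sit at the edge by construction, so the counts are not probabilities.

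**4. An equal share lost.** Suppose each failure in either arm leaves the PPS with probability f. At 93% against 98% and f = 0.05, the retained failure rates are 0.07 × 0.95/(1 - 0.07 × 0.05) = 6.67% and 0.02 × 0.95/(1 - 0.02 × 0.05) = 1.90%. The difference falls from 5.00 to 4.77 points. Enumerating both binomials at 189 per arm, with no other missing data, gives the chance of declaring non-inferiority:

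| f (assumed) | 93% v 98% | 98% v 98% |
|---|---|---|
| 0 | 3.9% | 91.9% |
| 0.01 | 4.1% | 92.0% |
| 0.02 | 4.2% | 92.2% |
| 0.05 | 4.8% | 92.7% |
| 0.10 | 6.0% | 93.5% |

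The 3.9% at f = 0, above the nominal 2.5%, comes from the Wald interval at these rates and not from this point.

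**The case against.** The best defense is that the sentence loosely summarizes Scenarios 1 and 4, and that the table, with its explicit PPS row, governs. The conflict needs one record to mix an adverse answer with an NA or blank item. The Protocol words questions 1-4 as yes/no questions, so a syringe that cannot be connected should be No, not NA. Protocol 8.5 provides data checks and queries. Such a record is Fail in the FAS under both texts, and SAP 6.2.1 lists subjects outside the PPS, so a dropped failure would be visible. All this stands, and it keeps the point small. But the SAP itself provides for NA answers, does not say that the table governs, and makes the PPS primary. Listings disclose an exclusion but do not prevent it.

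A reader might infer three stronger points that the documents do not support.

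- **That a use stopped for a device fault generally escapes the endpoint.** Protocol 5.5.2 says of faults that "if such problems are found after the priming preparation, each subject can only use the current one without changing the device", and that the use "shall be evaluated by the study nurse after flushing and/or locking the end of the catheter line". No rule names a stopped use as Fail. But question 3 answered plainly is No, question 5 covers a leak at any time, and Protocol 5.5.2 requires effectiveness to be recorded at the treatment visit. What remains is missing detail.
- **That Protocol 5.5.2 orders use of a faulty syringe.** Its natural meaning is that no second syringe is supplied. The cautions in Protocol 3.3.10, such as "Do not use if the pre-filled flush syringe is damaged and leaking", still apply, and Protocol 5.2.3.1 lets the investigator withdraw a subject.
- **That the SAP's code unsettles the FAS rule, because it recodes everything other than a pass as not pass.** That line belongs to the site-adjusted calculation, used when the Breslow-Day P is 0.05 or less, and its comment describes a two-valued variable. Table 6.1, SAP 6.1 and SAP 7.1 agree that a Missing outcome is not counted.

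**Conclusion.** The contradiction holds and is minor. It is confined to PPS membership of records that combine an adverse answer with an NA or blank item. Applying the sentence would remove recorded device failures from the primary analysis; applying the table would not.

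The frequency is unknown, since the documents give no rate of NA answers or early device faults. The loss shares and failure counts above are therefore assumptions. At shares of 1% to 5%, the chance of a wrong claim at 93% against 98% rises by roughly 0.2 to 0.9 points. A single test-arm record can decide a result at the boundary, but nothing suggests that the trial will land there. The direction depends on the pattern of loss: test-arm failures, or equal shares, favor non-inferiority; an equal count per arm does not bring the difference nearer zero.

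**What to change.** Amend SAP 6.3.1 only, before the data review meeting:

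1. State that any No on questions 1-4, or Yes on question 5, is Fail in both the FAS and the PPS, whatever the other items show.
2. Limit the exclusion sentence to Scenarios 1 and 4.

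Optionally, add that a use stopped for a device fault after priming is answered No on question 3.

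The cost is a short SAP revision. Sample size and procedures do not change, and the Protocol needs no amendment. The downside is that observed success rates may be slightly lower.
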